#### 6.2.3.2 Follow-up

Follow-up visits will be performed after the EOT visit in case a patient has completed treatment according to protocol or is not eligible for further treatment courses prior to administration of the maximum number of courses. Follow-up will end in case the patient is

- lost to follow-up
- receives new anti-lymphoma therapy
- withdraws consent
- in case the investigator and sponsor agree not to pursue further follow-up visits
- death

Follow-up visits should be performed at 6 weeks intervals or more frequent if appropriate. Follow-up visits should be done at the investigational site, but may be performed by telephone interview in case the patient is unable to visit the investigator. Follow-up visits should be performed up to 6 months after the end of treatment visit. At the last follow-up visit, an end of trial assessment will be performed and documented in the eCRF. For follow-up of patients with adverse events which have not recovered at the last planned follow-up visit please refer to [section 5.2.2.2](#).

The following will be obtained and / or performed (see [flowchart](#) for Course 3):

- Vital signs (see [section 5.2.5.1](#)), weight, physical examination

Proprietary confidential information.

© 2016 Boehringer Ingelheim International GmbH or one or more of its affiliated companies. All rights reserved.

This document may not - in full or in part - be passed on, reproduced, published or otherwise used without prior written permission.

- Disease assessment: clinical assessment of tumour size (lymph nodes, spleen, liver), imaging if applicable
- Changes in concomitant therapies
- Safety laboratory parameters as specified in [section 5.2.3.1](#)
- Adverse events
- CMV monitoring (see [section 5.2.3.3.2](#))
- Lymphocyte typing (see [section 5.2.3.4](#))
- Status of the patient: date of progression (in case, the patient experienced PD) date death (if applicable)
- Treatment with any other anti-lymphoma drug (report start date of treatment and therapy)

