Progression free survival (PFS) censored [in days] is therefore the time from first administration of study medication to the date of last response assessment (date of last response assessment – date of first administration of study medication + 1).

Failure free survival (FFS):

FFS is defined as the time from first administration of study medication until disease progression or death or start of next NHL therapy.

Patients not administered another NHL therapy and not presenting with disease progression or death during the trial will be censored at the date of the last response assessment during which the patient was evaluable and did not have the event.

The censoring rules and the applicable dates of outcome for FFS are given in the following table.

Table 5.2.2:2 Derivation rules for failure-free survival

Situation	Outcome (event or censored)	Date of outcome
Baseline and post-baseline disease assessment: disease progression or death or start of next NHL therapy	Event	Date of first disease progression or death or start of next NHL therapy
Baseline and post-baseline disease assessment: No disease progression, death or new NHL therapy	Censored	Date of last response assessment
No baseline or post-baseline disease assessment: no death or new NHL therapy	Censored	Date of first administration of BI 836826
No baseline or post-baseline disease assessment: death/next NHL therapy on or before the first planned disease assessment (i.e. week 4 assessment)	Event	Date of death/next NHL therapy
No baseline or post-baseline disease assessment: death/next NHL therapy after the first planned disease assessment (i.e. week 4 assessment)	Censored	Date of first administration of BI 836826

Remark: determination of the response status via disease assessment refers to any disease assessment via imaging or via physical assessment

Failure free survival (FFS) [in days] is therefore the time from first administration of study medication to the earlier of disease progression or death or start date of next NHL therapy. (minimum date of disease progression, death or start of next NHL therapy – date of first administration of study medication + 1).

Failure free survival (FFS) censored [in days] is therefore the time from first administration of study medication to the date of last response assessment (date of last response assessment – date of first administration of study medication + 1).

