6. GENERAL ANALYSIS DEFINITIONS

6.1 TREATMENTS

In this Phase I trial, treatments are not randomised (open-label, dose escalation). Different dose levels of BI 836826 can arise. The data will be presented for all dose cohorts separately, where Korean patients will be presented as a separate dose cohort from Caucasian patients.

In addition, the results for all patients in total, all Caucasian patients in total, and all Korean patients in total will be presented.

To justify the MTD determination, DLTs occurring during the MTD evaluation period (very first infusion of BI 836826 until the day of second infusion in Course 1 + seven days) will be presented separately from those occurring during the complete on-treatment period.

“Analysing treatment” will be used for reporting of treatment emergent AEs and to differentiate between screening, on-treatment and post-study safety data. The inequalities start date \leq onset date of AE $<$ end date will determine whether the AE will be assigned to the “analysing treatment” or not.

For the on-treatment period and the MTD evaluation period, the initial trial medication assigned at the beginning of the first treatment course will be used as the label of the analysing treatment.

AEs that have an onset date during the screening or post-study periods will be displayed in separate listings from those occurred during the on-treatment period.

The actual planned dose of trial medication administered on the day each AE started will also be derived. This will be presented in patient listings, but will not be used for defining treatments for analysis.

Labels of each analysing treatment period, analysis numbers, the labels used for display in the tables and listings in the CTR, as well as codes, decodes, sort order and labels for each trial medication used in this trial are provided in the TSAP technical document “ADS Plan”.

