7. PLANNED ANALYSIS

For end-of-text (EoT) tables, the set of summary statistics is: N / Mean / standard deviation [StD] / Minimum [min] / Median / Maximum [max].

For tables that are provided for endpoints with some extreme data, median, quartiles and percentiles should be preferred to mean, StD, min and max.

For time-to-event analysis tables, the set of statistics is: number of patients [N(%)], Number of patients with event [N(%)], <Time to event> [months] followed by P25 (25th percentile), median, P75 (75th percentile), Number of patients censored [N(%)]. If not specified otherwise, the duration as well as the time to event will be displayed in days and a final decision will be made at the last BRPM.

Tabulations of frequencies for categorical data will include all possible categories and will display the number of observations in a category as well as the percentage (%) relative to the respective treatment group (unless otherwise specified, all patients in the respective patient set whether they have non-missing values or not). Percentages will be rounded to one decimal place. The category missing will be displayed only if there are actually missing values. The denominator of the main categories is defined by the number of patients in the used patient set. The main categories define the denominators of the subcategories. Subcategories should be intended and “[N(%)]” will be displayed only for the main category. If a table includes only categorical data, “[N(%)]” is to be displayed in the column header.

If applicable, conversion from days to weeks, months and years will be as follows:

- Weeks = Days/7
- Months = (Days × 12)/365.25
- Years = Days/365.25

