for all analyses. In laboratory listings, the CTCAE grade will be displayed as -1.

Patients with hepatic enzyme elevation will be tabulated.

Patients with possibly clinically significant laboratory values will be tabulated (see [Section 9.2](#)).

The prioritized laboratory values (see [Section 5.4.5.1](#)) will be displayed in Section 15 of the final CTR while all other laboratory parameters will be displayed in the Appendix of the CTR.

Neutropenia, thrombocytopenia and leukopenia

Episodes of low neutrophil, platelet and WBC counts are of special interest. Episodes with CTCAE grade 3/4 as well as episodes with CTCAE grade 4 lasting 7 or more days will be analysed separately.

An episode of low blood counts of grade 4 starts with the first occurrence of a CTCAE grade 4 and lasts until the first time the CTCAE grade falls back to <=3 (analogously for an episode of CTCAE grade 3/4).

In case the episode starts during the EOT or Follow-up, the duration of this episode is defined to be missing. The reason for this approach is that after the EOT laboratory data is only

captured infrequently and therefore the duration of an episode would be overestimated due to lack of data.

If an episode starts before EOT and the CTCAE grade of the respective parameter does not fall back to the respective grade that ends the episode and the patient dies, the end of the episode is defined by the date of death. If the episode starts before EOT and lasts during Follow-up, the episode is censored with the date of DBL.

Number of patients with respective episodes, number of episodes, episodes per patient, duration of individual episode, number of episodes divided by number of infusion per patient, mean and median duration of episode per patient will be displayed.

Additionally, a frequency table displaying number of patients with episode of neutropenia Grade 4 and concomitant AEs in the UDAEC Infections (incl. respiratory infections and sepsis) of any grade as well as only for Grade 3 or 4 infections will be provided. In this context, concomitant AE is defined as AE with onset date within the neutropenia episode. This will be also done for CD4+ T-cell count Grade 4 and concomitant CD4 related specific infections from the UDAEC CD4 related specific infections.

The same way, a frequency table displaying number of patients with episode of thrombocytopenia Grade 4 and concomitant AEs in the UDAEC bleeding of any grade as well as only for Grade 3 or 4 bleeding will be provided.

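### Cytopenia episodes still open in follow-up are censored at database lock, an administrative date, with no rule for how censored durations enter the summaries

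*SAP*

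**What the plan says.** SAP 7.8.2 singles out low neutrophil, platelet and white-cell counts for episode analysis. An episode ends at the first return below the qualifying grade. Other cases are handled as follows:

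- Onset at or after EOT: duration is set to missing. The reason given is that laboratory data are sparse by then and "the duration of an episode would be overestimated due to lack of data".
- Onset before EOT, never resolved, patient dies: the episode ends at death.
- Onset before EOT and continuing into follow-up: "If the episode starts before EOT and lasts during Follow-up, the episode is censored with the date of DBL".

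The outputs include the duration of each episode, and "mean and median duration of episode per patient will be displayed". The available SAP text does not say whether a censored duration is counted as complete, left out, flagged or analysed by a time-to-event method. Section 7.5.2 names Kaplan-Meier only for PFS and FFS. Section 7 has a time-to-event table layout with a count of censored patients, but 7.8.2 does not call on it. Section 6.6, on missing data, is silent on censored durations.

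SAP 6.1 adds: "The data will be presented for all dose cohorts separately", with Korean patients kept apart from Caucasian patients.

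**The concern.** A duration should be censored at the last date on which the patient was known to be still in the episode. Database lock is set by trial administration. Protocol 6.2.3.2 says: "Follow-up visits should be performed up to 6 months after the end of treatment visit", and follow-up ends sooner if, for example, the patient "receives new anti-lymphoma therapy". Between the last count and lock the grade is unknown.

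The SAP's own reasoning points the other way. It discards durations of late-starting episodes because sparse sampling would inflate them, then extends earlier-starting episodes across a period with possibly no sampling at all. For PFS and FFS (section 5.2.2) it uses the sound rule: patients without an event "will be censored at the date of the last response assessment during which the patient was evaluable".

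The bias is also uneven. The time from last count to lock depends on when a patient enrolled, not on the drug, so earlier cohorts can show longer durations for the same observed course. Infections with grade 4 neutropenia prompted the lower-dose Korean cohorts (SAP 3), and Protocol 5.2.1.1 has haematological events considered for the further-development dose. Section 7.8.2 also counts an adverse event as concomitant if it starts within the episode. An episode taken to run to lock could absorb events with no count showing cytopenia at the time.

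**Working it through.** The plan gives no figure to reproduce. The check is date arithmetic on how much unobserved time the rule can add.

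**Inputs**
- Time to EOT: 26 weeks = 182 days (Protocol synopsis). Follow-up: 6 months, taken as 183 days (Protocol 6.2.3.2).
- Delay: up to 3 weeks (Protocol 6.1), applied once in each of three courses as an outer limit = 63 days.
- 37 escalation patients (SAP 3): first dose no later than the Phase I safety report of 13 February 2015 (Protocol 9.2).
- 4 Korean 100 mg patients: among the 41 enrolled (37 + 4; Protocol 7.6) at the amendment of 1 October 2015.
- Lock date is not given. Assumed no earlier than the SAP revision of 28 August 2017.
- Assumed: at most 12 administrations, and no counts after planned follow-up.

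**Longest planned span, first dose to last follow-up visit**
182 + 183 = 365 days; with delays, 365 + 63 = 428 days.

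**Gap from last possible planned count to lock**

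| Group | Latest first dose | Last planned visit (365 / 428 days) | Gap to 28 Aug 2017 |
|---|---|---|---|
| Escalation | 13 Feb 2015 | 13 Feb 2016 / 16 Apr 2016 | 562 / 499 days |
| Korean 100 mg | 1 Oct 2015 | 30 Sep 2016 / 2 Dec 2016 | 332 / 269 days |

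An earlier first dose, an earlier end of follow-up or a later lock makes these longer. Dosing dates for the Korean 50 and 75 mg patients are not given. With lock on 28 August 2017, their gap runs from zero (first dose on or after 26 June 2016 with full delays, or 28 August 2016 without) to about 332 days (first dose on 1 October 2015).

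**Illustration (assumed course)**
Onset is on day 22. A follow-up count 60 days later is still unresolved, and new therapy then ends follow-up. Observed duration: 60 days.
- Escalation: day 22 is 6 March 2015 at the latest; to 28 August 2017 = 906 days.
- Korean 100 mg: day 22 is 22 October 2015 at the latest; to 28 August 2017 = 676 days.

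If this is the patient's only episode, the within-patient mean and median are both 906 or 676.

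If a cohort mean is taken instead, and every other patient has one 10-day episode:

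| Cohort | Using the last count | Using lock |
|---|---|---|
| 6 escalation patients | (50 + 60)/6 = 18.3 | (50 + 906)/6 = 159.3 |
| 3 escalation patients | (20 + 60)/3 = 26.7 | (20 + 906)/3 = 308.7 |
| 4 Korean 100 mg patients | (30 + 60)/4 = 22.5 | (30 + 676)/4 = 176.5 |

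The cohort median is 10 days throughout.

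**Does a time-to-event method remove the problem?** No. Kaplan-Meier would keep the patient at risk, with no recovery, across time when recovery could not have been seen. That also pushes estimated duration upwards. The censoring date is wrong under either method.

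**The case against.** The best case for the plan is as follows.

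- **The value is labelled censored.** The SAP does not tell a programmer to treat it as complete, and section 7 has a suitable layout. This stands as far as it goes: averaging is a risk left open, not an instruction. The lock date remains wrong either way.
- **The rule may be elsewhere.** An internal laboratory guideline and some SAP sections are not available. Section 7.8.2 does not refer to any of them for this point, and an unseen summary rule would not change the stated date.
- **Counts may continue.** Protocol 5.2.2.2 follows all adverse events until recovery or sufficient characterisation, and SAEs and drug-related grade 3 events beyond the trial. A grade 4 cytopenia might well qualify, which could shorten the gap. However, a laboratory change becomes an adverse event only if judged clinically relevant (Protocol 5.2.2.1), so counts up to lock are not assured.
- **Extreme data are already addressed.** SAP 7 says: "median, quartiles and percentiles should be preferred to mean, StD, min and max". This protects a cohort median. It does not help a within-patient summary based on one episode.
- **Little is exposed, and the example is chosen.** The numbers of patients and episodes are unaffected, and so are the rates per patient and per infusion. Applying a delay only to courses 1 and 2, for which Protocol 6.1 states a maximum length, the lower escalation gap is 520 days rather than 499. Both points are fair, and neither changes the conclusion.

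**Conclusion.** The concern holds as a minor point. Lock is a wrong censoring date, at odds with the SAP's own overestimation argument and its PFS and FFS rules, and the available text does not say how censored durations are summarised.

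The wording defect is certain; its effect is not. The figures depend on the assumed lock date, the 12-administration limit and the absence of counts after planned follow-up. There may be no affected episodes. Exposure is limited to the descriptive duration outputs and possibly the concomitant-event tables. The MTD rests on non-haematological toxicity and is unaffected.

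**What to change.** In SAP 7.8.2:

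1. Keep first observed recovery and death as episode ends, and state that recovery seen at a follow-up visit counts. As written, the lock rule could be read to cover episodes that resolve during follow-up.
2. Otherwise censor at the last available value for that parameter, including unscheduled counts.
3. Flag censored durations in the listing, report how many there are, and do not average them as complete. Show them separately or, optionally, use the section 7 time-to-event layout on one episode per patient, such as the first or the longest.
4. Use the same end date for the concomitant-event window.

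The cost is one or two SAP sentences, a listing flag and minor programming. No new data are needed.

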## 6.2.2 Treatment periods

The treatment is given in courses with 4 administrations of a weekly infusion followed by observation/rest. Patients can receive up to three courses, *i.e.* 12 administrations. The duration of the first two courses is 7 weeks and for the third course 12 weeks, hence a 3-week or an 8-week observation/rest after the infusions of BI 836826.

### 6.2.2.1 Course 1

In the first course there are 4 visits with treatment and 6 visits for safety assessment. The first two administrations are given as an in-hospital stay for safety, tumour lysis assessment

Between the visits with infusion of BI 836826 safety visits will be performed. After last infusion the safety visits will be weekly. Clinical disease assessment will be performed at the first infusion visit (visit 1) and the last infusion visit (visit 7) as well as the last visit in the course (visit 10).

For details see [flowchart](#) for Course 1.

In case of the split first dose administration patients are required to be hospitalized under close surveillance with access to intensive care for at least 72 hours after the start of the low dose of BI 836826 to allow close monitoring for infusion-related reactions. Please refer the flowchart in [section 10.7](#) for clinical disease, safety

### 6.2.2.2 Course 2

In the second course there are 4 visits with treatment and 6 visits for safety and response assessment. The first administration is given as an in-hospital stay for safety, tumour lysis assessment

Between the visits with infusion of BI 836826 safety visits will be performed. After last infusion the safety visits will be weekly. Clinical disease assessment will be performed at the first infusion visit (visit 1) and the last infusion visit (visit 7). A CT scan of neck, thorax, abdomen and pelvis must be performed at visit 9 to be available for the disease assessment and response evaluation that are planned to be done at the last visit in the course 2 (visit 10).

For details see [flowchart](#) for Course 2.

### 6.2.2.3 Course 3

In the third course there are 4 visits with treatment and 5 visits for safety and response assessment. All infusions can be given as out-patient, if recent previous infusions have been well tolerated. Clinical disease assessment will be performed at the first (visit 1) and at the last infusion (visit 4).

Proprietary confidential information.

© 2016 Boehringer Ingelheim International GmbH or one or more of its affiliated companies. All rights reserved.

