3. INTRODUCTION

As per International Conference of Harmonisation, statistical principles for clinical trials, E9 (ICH E9), the purpose of this document is to provide a more technical and detailed elaboration of the principal features of the analyses described in the clinical trial protocol (CTP), and to include detailed procedures for executing the statistical analysis of the primary and secondary variables and other data.

This trial statistical analysis plan (TSAP) assumes familiarity with the protocol, including protocol amendments. In particular, the TSAP is based on the planned analysis specifications as written in CTP Section 7, “Statistical Methods and Determination of Sample Size”. Therefore, TSAP readers may consult the CTP for more background information on the study, e.g., on study objectives, study design and population, treatments, definition of measurements and variables, planning of sample size, randomisation. This TSAP follows the Boehringer Ingelheim (BI) internal reference ([1](#)).

The primary objective of this trial is to determine the maximum tolerated dose (MTD) of BI 836826 in patients with non-Hodgkin lymphoma (NHL) of B-cell origin. BI 836826 is a new biological entity and the maximum planned single dose is 1400 mg. If the MTD is not reached with this dose, an optimal biological dose (OBD) may be defined instead.

The MTD of BI 836826 was defined as 100 mg in this trial for Caucasian patients. This dose was declared based on safety demonstrated during the dose escalation which was performed in 37 Caucasian patients. The results have been reported in the “CTR – Phase I Safety Analysis Report” ([8](#)).

The planned additional expansion phase enrolled 4 patients (all 4 in Korea). After 3 of these 4 Korean patients developed significant toxicities (ie. infections associated with Grade 4 neutropenia), the protocol was amended for the need of exploring lower dose levels (50 mg and 75 mg) in a designated escalation cohort of Korean patients, with the aim of defining a MTD in Korean patients. Thus, the expansion phase on 100 mg had been stopped. Secondary objectives are the collection of overall safety and anti-tumour efficacy data and the determination of the profile of BI 836826.

In the following, study medication always refers to BI 836826.

SAS® Version 9.2 (or higher) will be used for all analyses.

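### The window pairing Grade 4 cytopenia with infection or bleeding follows sample dates, so events are misclassified at both ends; a sensitivity count is needed beside the strict one

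*SAP*

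**What the plan says.** SAP 7.8.2, in the part on neutropenia, thrombocytopenia and leukopenia, defines episodes by laboratory samples. A Grade 4 episode "starts with the first occurrence of a CTCAE grade 4 and lasts until the first time the CTCAE grade falls back to <=3". For episodes that do not resolve before end of treatment (EOT), the end is the date of death if the patient dies. Otherwise: "If the episode starts before EOT and lasts during Follow-up, the episode is censored with the date of DBL".

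The same section plans a frequency table of patients who have both a Grade 4 neutropenia episode and an infection, "of any grade as well as only for Grade 3 or 4 infections will be provided". The link between the two is the onset date: "concomitant AE is defined as AE with onset date within the neutropenia episode". There is no look-back to the previous sample and no separate closing date for this purpose. An infection already under way at the first Grade 4 sample is excluded by its onset date. The approach is repeated for thrombocytopenia with bleeding and for low CD4+ counts with CD4-related infections.

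The section does recognise sparse sampling as a problem, but only for duration. Episodes that begin at EOT or in follow-up have their duration set to missing, because infrequent samples would make it look too long. That reasoning is not carried over to the concomitance rule.

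**The concern.** Sample dates stand in for the true start and end of Grade 4, and both are late. A patient whose count falls after one visit, who becomes infected, and whose next sample shows Grade 4 has an infection onset before the episode opens and is not counted. A patient whose count recovers soon after a Grade 4 sample stays inside the window until the next sample, so an infection after recovery is counted. An episode left open to DBL extends this second error much further.

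The pairing matters in this trial. SAP section 3 describes the toxicities in 3 of the 4 Korean patients at 100 mg as "infections associated with Grade 4 neutropenia", and these events led to the lower-dose Korean cohorts. In the SAP text available, these are the only tables that link cytopenia episodes to clinical events in time. Korean patients are shown as separate cohorts (SAP 6.1), with 3 to 6 patients at each new dose. One misclassified patient moves the reported proportion by 1/6 = 17 percentage points in a cohort of six and 1/3 = 33 points in a cohort of three.

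**Working it through.** The documents give no figure for this rule, so there is none to reproduce. The check applies the SAP definition to the visit schedule.

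**Inputs from the documents**
- Course 2 sampling days (Protocol, flowchart for course 2): 1, 2, 3, 8, 15, 17, 22, 29, 36, 43. The gaps are 1, 1, 5, 7, 2, 5, 7, 7, 7 days, before visit windows. Protocol 6.2.2 confirms the later part: "After last infusion the safety visits will be weekly". Course 1 is assumed to follow the same pattern; 6.2.2.1 gives it the same number of visits.
- Course 3 (flowchart for course 3): weekly to day 43, then days 57 and 71, so gaps of 14 days. Both of these visits have a window of ±5 days, so they can be up to (71 + 5) − (57 − 5) = 24 days apart.
- Follow-up (Protocol 6.2.3.2): "Follow-up visits should be performed at 6 weeks intervals or more frequent if appropriate", so about 42 days.

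**Assumptions, not in the documents**
- True Grade 4 duration D is 7, 14 or 21 days.
- Grade 4 onset is uniform in time.
- The infection rate is constant during Grade 4, and lower after recovery by a factor RR of infinity (no infections after recovery), 5, 2 or 1.
- Only scheduled samples are taken.

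**Step 1: unseen lead-in.** The mean wait from a random onset to the next sample is Σg² / (2Σg) = 252 / (2 × 42) = 3.0 days. When no gap exceeds D, the share of infections lost is 3.0/D: 43%, 21% and 14% for D = 7, 14 and 21. A simulation on the schedule (200,000 episodes per scenario) gives a lead-in of 2.9 days and losses of 42%, 21% and 14%. A constant 7-day gap would give 3.5 days and 50%, 25% and 17%, which is too high because gaps are shorter around the infusions.

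**Step 2: late close.** In the same simulation the window overruns the true end by 3.1 days on average (3.2 days at D = 21).

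**Step 3: net count relative to truth.** Ratio = (D − lead-in + overrun/RR) / D. For D = 14 and RR = 2: (14 − 2.93 + 3.10/2) / 14 = 12.62/14 = 0.90. Results for courses 1 and 2:

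| D (days) | Lost at the start | Net, RR = ∞ | Net, RR = 5 | Net, RR = 2 | Net, RR = 1 |
|---|---|---|---|---|---|
| 7 | 42% | 0.58 | 0.67 | 0.80 | 1.02 |
| 14 | 21% | 0.79 | 0.84 | 0.90 | 1.01 |
| 21 | 14% | 0.86 | 0.89 | 0.94 | 1.01 |

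**Step 4: late course 3.** With gaps of 7 to 14 days, 68%, 42% and 28% are lost for D = 7, 14 and 21. About 30% of the 7-day episodes are never sampled at all. The net ratios run from 0.32 to 1.09, 0.58 to 1.15 and 0.72 to 1.00 across the RR values.

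**Step 5: the DBL rule.** It is not in these figures. It can only add counted infections, so it pushes every net ratio upwards.

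The figures apply to counts taken with the general safety laboratory (neutrophils, platelets). CD4+ counts follow the lymphocyte-typing schedule and were not modelled.

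**The case against.** The strongest reply is that this is a minor feature of one set of descriptive tables. Requiring onset after a documented Grade 4 value preserves the order of events, whereas a look-back will admit infections that came first. Patients who become ill will often have unscheduled counts. Protocol 4.1.4.3 relies on frequent blood counts, 4.1.4.4 requires laboratory review before each infusion, and 5.2.3.1 asks for at least weekly visits when a course is delayed for an adverse event. Each of these shortens the lead-in. The tables count patients, so someone with a second qualifying infection is still counted. The 14-day gaps start three weeks after the last course 3 infusion and concern only patients who reach that course.

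Most of this stands, and it limits the size. It does not remove the lead-in: symptoms can precede even an unscheduled sample, and 7.8.2 has no rule for that case.

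A reader might also infer that the MTD or the closure of the 100 mg cohort depends on this window. The documents do not support that. The MTD rests on DLTs (SAP 5.1 and 7.4), infection due to neutropenia falls under the DLT definition whatever the window (Protocol 5.2.1.1), and the 100 mg expansion had already stopped. Infections are also reported in the general adverse event and user-defined category tables, although those do not show timing against the counts.

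**Conclusion.** The point holds as two-sided misclassification. At the opening, under scheduled sampling and true durations of 7, 14 and 21 days, about 42%, 21% and 14% of infections truly starting in Grade 4 are lost in courses 1 and 2. At the close, about 3 days beyond true recovery are included, and much more for episodes left open to DBL. How much the DBL rule adds cannot be sized. It depends on the number of open episodes and on whether the table is confined to on-treatment adverse events, which 7.8.2 does not state.

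Two stronger readings are tempting, and neither is supported:
- That infections starting between samples are missed in general. Only the gap before the first Grade 4 sample is lost, plus short episodes never sampled. Onsets between two Grade 4 samples, or between the last Grade 4 sample and the first recovered one, are counted.
- That the link between neutropenia and infection is certainly understated. The late close and the DBL rule work the other way. In courses 1 and 2 the net ratio is 0.58 to 0.94 when risk is at least doubled during Grade 4, but 1.01 to 1.02 when it is not raised, before any effect of DBL. The table also has no comparison rate outside neutropenia, so it estimates no association that could be biased.

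All sizes depend on the assumed durations, hazards and sampling. The change is worth making because the cohorts are small and the cost is low.

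**What to change.** Keep the strict count as defined and add a sensitivity column beside it in each concomitance table:
- **Opening:** the day after the last sample of grade 3 or lower, with a look-back cap that covers the scheduled gap: 7 days in courses 1 and 2, 14 days in late course 3.
- **Close:** the first recovered sample. If there is none, use the last available on-treatment sample or death, not DBL.
- **Scope:** the same rule for thrombocytopenia with bleeding and for CD4+ counts with CD4-related infections. For CD4+, tie the cap to the lymphocyte-typing schedule.

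A footnote should give the number of patients added by the earlier opening and the number removed by the earlier close, since the two changes act in opposite directions.

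The cost is one date derivation and one column, from data already collected. The downside is that some events that began before the count reached Grade 4 will be included. In courses 1 and 2 the wider window exceeds the true episode by about 3 days at each end, so it leans towards over-counting. This is why it belongs beside the strict count and should not replace it.
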